8.3.3 Appropriateness of efficacy assessments

MS relapse, EDSS assessments as well as MRI parameters in this patient population are standard efficacy assessments in MS and serve to characterize the patient population included in this study as well as their disease activity and neurological status over the study.

8.4 Safety

Safety assessments are specified as below with the assessment schedule detailing when each assessment is to be performed. If the COVID-19 pandemic limits or prevents on-site study visits, phone calls or virtual contacts should be conducted for safety monitoring and discussion of the participant's health status, until the participant can again visit the site. In exceptional cases and after discussing with Novartis, safety tests could be performed outside of the investigator sites.

For details on AE collection and reporting, refer to AE section.

- Physical/neurological examination
- Vital signs
- Skin assessments
- Laboratory evaluations
- ECG
- First dose monitoring
- Ophthalmologic exams / Optical coherence tomography (OCT)
- Pulmonary function test

As per Section 4.6, during a Public Health regular phone or virtual calls can occur (every 12 weeks or more frequently if needed) for safety monitoring and discussion of the participant's health status until it is safe for the participant to visit the site again.

Table 8-2 Assessments & Specifications

Assessment	Specification
Physical	A physical examination may be performed at a scheduled visit and may include an assessment of skin, head and neck, lymph nodes, breast, heart, lungs, abdomen, back and/or comments on general appearance. A neurological examination may also be a part of the physical examination. Information for all physical examinations must be included in the source documentation at the study site. Clinically relevant findings that are present prior to signing informed consent must be recorded on the appropriate CRF that captures medical history. Significant findings made after signing informed consent which meet the definition of an Adverse Event must be recorded as an adverse event.
Vital signs	Vital signs include temperature, blood pressure and pulse measurements. Sitting pulse rate and blood pressure will be recorded at each visit and should be obtained after the patient has 5 minutes of rest. The pulse should be measured just prior to obtaining the blood pressure measurement. After the participant has been sitting for five minutes, with back supported and both feet placed on the floor, systolic and diastolic blood pressure will be measured three times using an automated validated device, e.g. OMRON, with an appropriately sized cuff. The

Assessment	Specification
	
repeated sitting measurements will be made at 1 - 2 minute intervals and the mean of the three measurements will be used.
 
Clinically notable vital signs are defined in Appendix 1.

Skin assessments	
A complete skin examination will be performed by a dermatologist or qualified physician as described in Table 8-1. The purpose of a skin examination at baseline is to exclude participants with suspicious skin lesions (pre-cancerous, cancerous) from the study and to document a baseline assessment in order to monitor participants with non-suspicious lesions for the duration of the study.
 
It is recommended that all participants perform a skin self examination (SSE) on a monthly basis. Participants should be instructed on how to properly conduct these examinations. If the participant reports new or changed lesion(s) during the study, a skin exam should be performed by a dermatologist.
 
In case of findings at any visit, suspicious for being precancerous or cancerous skin disorders, the investigator will refer the participant to a qualified physician for further examination and a biopsy may be required to rule out or to confirm diagnosis. Upon completion of the examination any new findings during the study will be transcribed in the Adverse Event eCRF.

8.4.1 Laboratory evaluations

Laboratory samples will be collected as described in [Table 8-3](#) and analyzed by the local lab. Investigators will be asked to comment on these abnormalities on the respective lab result page, including a notation of the clinical significance of each abnormal finding in the participant's source documents. The laboratory sheets will be filed with the source documents. Mandatory hematology and chemistry test results should be recorded on the eCRF.

Any diagnosis (or signs or symptoms if a diagnosis is not possible) associated with the abnormal findings should be recorded on the adverse event eCRF.

Clinically notable laboratory findings are defined in Appendix 1.

In case of increases in liver function test (LFT), refer to Appendix 7 Guidance on Safety Monitoring.

In case of decreases in lymphocytes, refer to Guidance on monitoring of participants with notable lymphopenia in Appendix 7 Guidance on Safety Monitoring.

If the COVID-19 pandemic limits or prevents on-site study visits, the method of collection of samples may be modified by Novartis if applicable and if modified, will be communicated to the Investigator. In exceptional cases and after discussing with Novartis, safety tests could be performed outside of the investigator sites.

Table 8-3 Laboratory Evaluations

Test Category	Test Name
Hematology	Hemoglobin, Platelets, White blood cells (WBC), Differential (Basophils, Eosinophils, Lymphocytes, Monocytes, Neutrophils, Other)

Test Category	Test Name
Hepatitis B test	HBV surface antigen, surface antibody, E antigen, E antibody, core antibody; if abnormal finding on HBV surface antigen, HBV DNA copies test will be performed.
Coagulation Function	Prothrombin time
Chemistry	ALT , AST , Creatinine, Direct Bilirubin, Total Bilirubin, Total Cholesterol
Urinalysis	Macroscopic Panel /Dipstick (Color, Blood, Glucose)
Additional tests	HIV antibodies
Pregnancy Test	Serum / Urine pregnancy test

8.4.2 **Electrocardiogram (ECG)**

ECGs will be collected at Screening visit, Day1, Month 1, Month 3, Month 6, Month 12, Month 18, Month 24, Premature discontinue from treatment (EOT), premature discontinue from study (EOS), Follow-up visit according to the assessment schedule and as needed if study drug is restarted after interruption.

At Day1, two to three ECGs will be performed. The first ECG will be performed on Day 1 to check the I/E criteria again. If the participant is eligible to be enrolled, the ECG result will be recorded as pre-dose ECG. The second ECG will be performed approximately 6-hours post-first-dose. If extended monitoring is needed, then a third ECG will be performed by the end of extended monitoring.

If study drug treatment is interrupted and treatment re-initiation meets the requirement for observation, the above procedures will be repeated, identical to procedures conducted at Day 1.

For any ECGs with participant safety concerns, an additional ECG must be performed to confirm the safety finding. Clinically significant abnormalities must be recorded on the CRF as adverse events.

All the below ECG parameters will be captured in the eCRF: heart rate, PR interval, QRS duration, QT and QTc interval. Any diagnoses (or signs or symptoms if a diagnosis is not possible) associated with the abnormal findings should be recorded on the adverse event eCRF.

8.4.3 **Pregnancy and assessments of fertility**

To confirm an eligibility of a woman of child bearing potential for the study, a blood pregnancy test should be performed at Screening visit. Participants, who are determined and documented to be surgically-sterile or post-menopausal for 12 months or longer prior to Screening, are not required to undergo pregnancy testing.

Women of child-bearing potential, defined as all women physiologically capable of becoming pregnant, including women whose career, lifestyle, or sexual orientation precludes intercourse with a male partner and women whose partners have been sterilized by vasectomy or other means, unless they meet the following definition of post-menopausal: 12 months of natural

(spontaneous) amenorrhea or 6 months of spontaneous amenorrhea with serum follicle-stimulating hormone (FSH) levels >40 mIU/m or 6 weeks post surgical bilateral oophorectomy with or without hysterectomy OR are using one or more of the following highly effective contraception: surgical sterilization, hormonal contraception, and double-barrier methods. Acceptable methods of contraception may include total abstinence at the discretion of the investigator in cases where the age, career, lifestyle, or sexual orientation of the participant ensures compliance. Periodic abstinence (e.g., calendar, ovulation, symptothermal, post-ovulation methods) and withdrawal are not acceptable methods of contraception. Reliable contraception should be maintained throughout the study and for 2 months after study drug discontinuation.

Additional Urine or Serum Pregnancy tests may be performed at scheduled assessment visit. The positive urine test needs to be confirmed with serum test.

Medical documentation of oophorectomy, hysterectomy, or tubal ligation must be retained as source documents. Subsequent hormone level assessment to confirm the woman is not of child-bearing potential must also be available as source documentation in the following cases:

1. Surgical bilateral oophorectomy without a hysterectomy
2. Reported 12 months of natural (spontaneous) amenorrhea with an appropriate clinical profile.

In the absence of the above medical documentation, FSH testing is required of any female participant regardless of reported reproductive/menopausal status at screening/baseline.

During a Public Health emergency as declared by Local or Regional authorities i.e. pandemic, epidemic or natural disaster, that limits or prevents on-site study visits, if participants cannot visit the site to have urine or serum pregnancy tests, urine pregnancy test kits for home use may be used if allowed by local regulations. Relevant participants can perform the urine pregnancy test at home and report the result to the site. It is important that participants are instructed to perform the urine pregnancy test first and only if the test result is negative proceed with the administration of the study treatment. A communication process should be established with the participant so that the Site is informed and can verify the pregnancy test results (e.g., following country specific measures).

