1.2 Purpose

The purpose of this study is to collect 24-month efficacy, safety, tolerability, and health outcome data of fingolimod (0.5 mg per Day) in participants with relapsing multiple sclerosis (RMS) in China. This is a post approval commitment study for fingolimod.

2 Objectives and endpoints

Table 2-1 Objectives and related endpoints

Objective(s)	Endpoint(s)
Primary objective(s)	Endpoint(s) for primary objective(s)

To evaluate the efficacy of fingolimod 0.5mg on annualized relapse rate (ARR) in	
Annualized relapse rate(ARR)

Objective(s)	Endpoint(s)
participants with RMS treated for up to 24 months.	
Secondary objective(s)	Endpoint(s) for secondary objective(s)

To evaluate the safety and tolerability of fingolimod 0.5 mg in participants with RMS treated for up to 24 months.To evaluate the efficacy of fingolimod 0.5 mg on MRI lesions.	
Adverse events (AE) and serious adverse events (SAE)Laboratory tests(hematology, biochemistry)Vital signsElectrocardiogram (ECG)Ophthalmology 
T1 hypo-intense lesion number and volume; T2 lesion volume, new/newly enlarged T2 lesion number; Gd-enhancing T1 lesion number and volume.

3 Study design

This is a 24-month, open-label, multicenter, interventional, single-arm study to collect efficacy, safety and health outcome data of fingolimod (Gilenya) 0.5 mg/day in approximately 100 relapsing multiple sclerosis (RMS) participants in China.

The study will consist of three Phases (see [Figure 3-1](#)):

Screening (up to 1 month): After signing informed consent, participants will enter a Screening Phase to determine eligibility according to inclusion and exclusion criteria.

[figure not shown]
The investigator must ensure that all patients meet the inclusion and exclusion criteria to be eligible to enter the study.

Treatment Period (24 months): On visit Day 1, all eligibility criteria will be confirmed, including a pre-dose ECG and vital signs. The first dose of study drug will be taken in the clinic on Day 1 and the participant will be monitored for at least 6 hours after the first dose administration before discharge. Refer to [Section 16.5](#) for Guidance for monitoring of patients taking their first dose of the study drug.

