Days	-30	1 to 1	27 to 33	87 to 93	175 to 185	265 to 275	355 to 365	445 to 455	535 to 545	625 to 635	715 to 725	NA	NA	775 to 785	
Informed consent	X														
Demography	X														
Inclusion / Exclusion criteria ⁶	X	X													
MS history/current medical conditions ⁷	X														
Concomitant medications	X	X	X	X	X	X	X	X	X	X	X	X	X	X	
Drug dispensation ¹		X	X	X	X	X	X	X	X	X					
Drug accountability ¹			S	S	S	S	S	S	S	S	S	S	S	S	
1st dose observation ⁸		X													
Pregnancy and assessments of fertility ⁹	S		S	S	S	S	S	S	S	S	S	S	S	S	
Body Height	X														
Body Weight	X			X	X	X	X	X	X	X	X	X	X	X	
Vital Signs	X	X	X	X	X	X	X	X	X	X	X	X	X	X	
Physical Examination	S	S			S		S		S		S	S	S	S	
MS relapse ¹⁰			X	X	X	X	X	X	X	X	X	X	X	X	
EDSS	X														
MRI ¹¹	X						X				X	X	X	X ⁵	
Ophthalmic examination ¹²	X			X	X		X				X	X	X	X	
Dermatological examination	S				S		S		S		S	S	S	S	
Electrocardiogram (ECG) ¹³	X	X	X	X	X		X		X		X	X	X	X	
Hematology	X		X	X	X	X	X		X		X	X	X	X	

Period	Screening	Treatment Period													Follow-up Visit ²
Visit Name	Screening	Day 1	Month 1	Month 3	Month 6	Month 9	Month 12	Month 15	Month 18	Month 21	Month 24	EOT ³	EOS ⁴	Follow-up Visit	
Days	-30	1 to 1	27 to 33	87 to 93	175 to 185	265 to 275	355 to 365	445 to 455	535 to 545	625 to 635	715 to 725	NA	NA	775 to 785	
HIV screen	S														
Chemistry	X		X	X	X	X			X		X	X	X	X	
Hepatitis B test ¹⁴	S														
Chest CT (Computed Tomography)	S														
Prothrombin time	S														
Urinalysis	S		S	S	S	S	S	S	S	S	S	S	S	S	
Reported AE/SAE		X	X	X	X	X	X	X	X	X	X	X	X	X	
Pulmonary function tests	S	as needed	as needed	as needed	as needed	as needed	as needed	as needed	as needed	as needed	As needed	As needed	As needed	as needed	

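### The only pregnancy test specified before the first fingolimod dose is a Screening blood test that may be 30 days old; Day 1 is the one blank column in the pregnancy row of Table 8-1

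*Protocol*

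**What the plan says.** - **Test before dosing.** Protocol 8.4.3 reads: "To confirm an eligibility of a woman of child bearing potential for the study, a blood pregnancy test should be performed at Screening visit". Section 8.3.2 puts the Screening visit up to 30 days before Day 1, and Section 3 allows up to one month for screening.
- **Schedule.** The Table 8-1 row "Pregnancy and assessments of fertility" has S at Screening, nothing at Day 1, and S at Months 1, 3, 6, 9, 12, 15, 18, 21 and 24, EOT, EOS and Follow-up.
- **Later tests.** Section 8.4.3 says: "Additional Urine or Serum Pregnancy tests may be performed at scheduled assessment visit". It adds: "The positive urine test needs to be confirmed with serum test".
- **Day 1 check.** Section 3 says: "On visit Day 1, all eligibility criteria will be confirmed, including a pre-dose ECG and vital signs". Section 8.4.2 says: "The first ECG will be performed on Day 1 to check the I/E criteria again". Pregnancy is part of exclusion 14 in Section 5.2.
- **Home testing in a public health emergency.** Section 8.4.3 has participants "perform the urine pregnancy test first and only if the test result is negative proceed with the administration of the study treatment".

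**The concern.** Day 1 is the visit at which drug exposure begins, and it is the only visit with no mark in the pregnancy row. The Day 1 eligibility check names an ECG and vital signs as its means, but nothing for pregnancy, so exclusion 14 could be re-confirmed on history alone. A woman who conceived after the Screening test and had not noticed could receive the first dose.

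The protocol itself treats this exposure as important. Section 4.5 warns of unknown risks to the fetus, and Section 9.1.1 makes pregnancy a mandatory reason to stop treatment. Stopping does not end exposure at once, because Section 8.4.4.4 says elimination may take up to two months.

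**Working it through.** The plan gives no figure of its own on this point. The check has three parts.

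**1. Is the blank cell really Day 1?** Table 8-1 has 14 visit columns: Screening, Day 1, nine monthly visits, EOT, EOS and Follow-up. The Vital Signs row fills all 14. The pregnancy row reads S, blank, then 12 times S, so the blank falls under Day 1. The Urinalysis row has the same pattern.

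**2. How old can the test be?** SAP 2.1.1 uses no Day 0.
- Day -30 to Day 1: 30 days.
- Day 1 to the Month 1 visit (Days 27 to 33): 26 to 32 days.
- From a Day -30 test to the next marked assessment: 30 + 26 = 56 to 30 + 32 = 62 days.
- A pregnancy first found at Month 1 would have had 26 to 32 days of dosing, plus up to about 60 days of elimination.

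**3. How many pregnancies could a Day 1 strip find?** Inputs not in the documents, and therefore assumed: 50 women of child-bearing potential (about 100 participants are planned in all), the yearly failure rate, and the lag L from conception to a positive urine strip (14 days, range 7 to 21). Section 5.2 mentions a failure rate below 1% for other forms of hormonal contraception; 1% is used as the base case, with 5% and 10% as a stress range.

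Conceptions in the gap = women × yearly rate × 30/365. At 1%: 50 × 0.01 × 30/365 = 0.041.

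Share a strip can find = (30 − L)/30: 77% for L = 7, 53% for L = 14, 30% for L = 21.

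| Yearly rate | In the 30-day gap | Found, L = 7 | Found, L = 14 | Found, L = 21 |
|---|---|---|---|---|
| 1% | 0.041 | 0.032 | 0.022 | 0.012 |
| 5% | 0.205 | 0.158 | 0.110 | 0.062 |
| 10% | 0.411 | 0.315 | 0.219 | 0.123 |

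Varying the number of women as well, conceptions in the gap run from 0.025 (30 women at 1%) to 0.82 (100 women at 10%). Thirty days is the maximum gap. With a shorter gap the yield falls, and once the gap is no longer than L the strip finds none of the conceptions within it.

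False positives, at an assumed 0.5% to 2%: 50 × 0.005 = 0.25 to 50 × 0.02 = 1 delayed first dose.

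**The case against.** **The footnotes may settle it.** The pregnancy row carries footnote 9 and the eligibility row footnote 6, and neither is in the text available here. A pre-dose rule could well sit there. This objection stands as a limit on certainty, and the fix is conditional on it. The blank Day 1 cell is still positive evidence that no test is scheduled at that visit.

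**Later tests look optional, but that goes too far.** A reader might infer from the permissive wording in 8.4.3 that every test after Screening is optional. The documents do not support this. All 12 later columns are marked S, and Section 8 says Table 8-1 lists the assessments scheduled at each visit. S does not signal an optional item: the Screening pulmonary function test is marked S, while 8.4.4.3 has it performed in all patients. The accurate statement is that text and table differ on whether later tests are required.

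**Day 1 is partly covered.** The eligibility check includes exclusion 14, contraception is an entry condition (with three months on a stable pill for oral users), and an investigator may test at any scheduled visit. All of this lowers the risk, but none of it requires a test.

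**The home-testing rule is a weak precedent.** It applies when site visits are impossible, so it does not show that the protocol breaks a rule of its own at the first clinic dose. It only supplies usable wording.

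**The benefit is tiny.** This is correct. The higher failure rates are also speculative. They are prompted by the 8.4.3 list of "surgical sterilization, hormonal contraception, and double-barrier methods", but double-barrier methods are not among those listed under exclusion 14, which governs entry. At the 1% rate, a false-positive delay is likelier than a true find. The two outcomes are unequal, though: a postponed dose against fetal exposure.

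**Conclusion.** The point holds as a schedule gap in the text available. One pregnancy test is specified before the first dose, it may be 30 days old, and the visit at which dosing starts is the only one without a mark. It is not a contradiction, and it affects no endpoint, sample size or analysis.

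It would be tempting to conclude that the plan lets women start treatment with pregnancy unchecked. The documents do not support that, since exclusion 14 is re-confirmed on Day 1 and a footnote may specify how.

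The expected gain is about 0.02 pregnancies found in the whole study, resting on three assumptions: 50 women, 1% a year and a 14-day lag. This illustrates the scale and is not a bound. The point ranks as a cheap improvement.

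**What to change.** First read footnotes 6 and 9 of Table 8-1. If either already requires a negative test before the first dose, nothing needs to change.

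Otherwise, mark a urine pregnancy test for women of child-bearing potential in the Day 1 column, and add one sentence to 8.4.3: the first dose is given only after a negative Day 1 result, and a positive strip is confirmed by serum before any decision. Serum confirmation is already in 8.4.3.

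The cost is one table mark, one sentence and one urine strip per woman, at a visit that already lasts at least six hours. The downside is an occasional first dose held until the serum result, about 0.25 to 1 among 50 women under the assumed false-positive rates. The strip would reduce inadvertent exposure without eliminating it, because conceptions in the days just before Day 1 would still be missed. If all participants have already started treatment, the change matters only for reuse of this schedule.

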	
2. Patients treated with any other investigational drug for MS in the period.3. Pregnant or nursing woman or woman of child-bearing potential not using effective contraception.4. Patient intolerant to undergo MRI or presents contraindications to MRI (e.g., metallic implants, metallic foreign bodies, pacemaker, defibrillator) and the use of gadolinium-based agents (e.g. people with severe kidney failure, patients with previous severe allergic/anaphylactoid reaction to a gadolinium-based contrast agent; patients with severe renal disease ((Estimated Glomerular Filtration Rate (eGFR) <30 mL/min/1.73 m²),) or acutely deteriorating renal function, who would be at risk of nephrogenic systemic fibrosis).5. Pediatric participant without confirmed history of chickenpox or confirmed documentation of a full vaccination course against varicella zoster virus (VZV).6. Any disability that may prevent the participants from completing all study requirements, as assessed by the treating physician (e.g., mental disorder, blindness or deafness that is not appropriate for age, severe language difficulty).7. Current medical or neurological condition that might impact efficacy assessments e.g. dementia, schizophrenia, bipolar disorder, major depression, history of multiple traumatic brain injuries, alcohol/drug abuse or dependence currently, or dependence within the last two years.
Study treatment	Fingolimod 0.5mg will be administered daily treated for up to 24 months.
Efficacy assessments	
• MS relapse• [REDACTED]• Magnetic Resonance Imaging (MRI)
Key safety assessments	
• Physical/neurological examination• Vital signs• Skin assessments• Laboratory evaluations• ECG• First dose monitoring• Ophthalmologic exams / Optical coherence tomography (OCT)• Pulmonary function test
Other assessments	[REDACTED]
Data analysis	All data will be analyzed using with summaries and/or statistical models appropriately. Annualized relapse rate (ARR) will be analyzed using a negative binomial model. Number and proportion of patients with new and newly enlarged T2 lesions will be statistically summarized as well as the number and proportion for patients with Gd-enhanced T1 lesions and the change of volume of T1 hypo-intense lesions from baseline. All safety [REDACTED] will also be statistically summarized appropriately.
Key words	Multiple sclerosis, relapse, efficacy, safety

1 Introduction

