5.2 Exclusion criteria

Participants meeting any of the following criteria at screening will not be eligible for this study.

1. History of myocardial infarction, unstable angina pectoris, stroke/transient ischemic attack, decompensated heart failure with hospitalization or New York Heart Association (NYHA) Class III/IV heart failure (refer to [Section 16.2](#) in the previous 6 months).
2. Treatment with Class Ia or Class III anti-arrhythmic drugs.
3. History or presence of Mobitz Type II 2nd degree or 3rd degree AV block or sick sinus syndrome, unless the participant has a pacemaker.
4. Screening and Baseline QTc interval \geq 500 msec.
5. History of symptomatic bradycardia or recurrent syncope.
6. History of cardiac arrest, uncontrolled hypertension or severe sleep apnea.
7. Macular edema during screening visit.
8. Increased risk for opportunistic infections, including immunocompromised participants :
 - currently receiving immunosuppressive therapies
 - immunocompromised by prior therapies where in the respective approved medication labels suggested wash out of the previous ongoing MS Disease Modifying Therapies (DMT) is not being conducted prior to ICF
 - absolute lymphocyte count is below $0.2 \times 10^9/L$
9. Known active malignancies.
10. Use of teriflunomide within 3.5 months prior to baseline, except if active washout (with either cholestyramine or activated charcoal) was done prior to fingolimod first dose in study.
11. Under MS investigational drug clinical study.
12. Severe active infections, active chronic infections (hepatitis, tuberculosis), as assessed by the treating physician.
13. Severe liver impairment (Child-Pugh class C).
14. Pregnant or nursing woman or woman of child-bearing potential not using highly effective contraception.

Women of child-bearing potential, defined as all women physiologically capable of becoming pregnant. Highly effective contraception methods include:

- Total abstinence (when this is in line with the preferred and usual lifestyle of the

participant. Periodic abstinence (e.g. calendar, ovulation, symptothermal, post-ovulation methods) and withdrawal are not acceptable methods of contraception.

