- Female sterilization (have had surgical bilateral oophorectomy with or without hysterectomy), total hysterectomy, or bilateral tubal ligation at least six weeks before taking study treatment. In case of oophorectomy alone, only when the reproductive status of the woman has been confirmed by follow up hormone level assessment.
- Use of oral, (estrogen and progesterone), injected, or implanted hormonal methods of contraception or placement of an intrauterine device (IUD) or intrauterine system (IUS), or other forms of hormonal contraception that have comparable efficacy (failure rate < 1%), for example hormone vaginal ring or transdermal hormone contraception.

In case of use of oral contraception women should have been stable on the same pill for a minimum of 3 months before taking study treatment.

Women are considered post-menopausal if they have had 12 months of natural (spontaneous) amenorrhea with an appropriate clinical profile (e.g. age appropriate history of vasomotor symptoms)). Women are considered not of child bearing potential if they are post-menopausal or have had surgical bilateral oophorectomy (with or without hysterectomy), total hysterectomy or bilateral tubal ligation at least six weeks ago. In the case of oophorectomy alone, only when the reproductive status of the woman has been confirmed by follow up hormone level assessment is she considered not of child bearing potential.

15. Pediatric participant without confirmed history of chickenpox or confirmed documentation of a full vaccination course against varicella zoster virus.
16. Any disability that may prevent the participants from completing all study requirements, as assessed by the treating physician (e.g., mental disorder, blindness or deafness that is not appropriate for age, severe language difficulty).
17. Current medical or neurological condition that might impact efficacy assessments e.g. dementia, schizophrenia, bipolar disorder, major depression, history of multiple traumatic brain injuries, alcohol/drug abuse or dependence currently, or dependence within the last two years.

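### Exclusion criterion 14 and Protocol Section 8.4.3 give different lists of highly effective contraception and different definitions of post-menopausal status

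*Protocol*

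**What the plan says.** Protocol Section 5.2, criterion 14, excludes any "Pregnant or nursing woman or woman of child-bearing potential not using highly effective contraception". It then sets its terms: "Women of child-bearing potential, defined as all women physiologically capable of becoming pregnant. Highly effective contraception methods include" total abstinence, female sterilization, hormonal methods, and intrauterine devices or systems. Other hormonal forms are admitted if their failure rate is below 1%. On menopause it says: "Women are considered post-menopausal if they have had 12 months of natural (spontaneous) amenorrhea", with a fitting clinical profile. Only post-menopausal or surgically sterile women are placed outside child-bearing potential.

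Section 8.4.3 (Pregnancy and assessments of fertility) starts from the same broad definition of child-bearing potential and then opens an exception with the word *unless*. The exception covers 12 months of natural amenorrhea, or 6 months with FSH above 40, or 6 weeks after bilateral oophorectomy. It continues: "OR are using one or more of the following highly effective contraception: surgical sterilization, hormonal contraception, and double-barrier methods". The paragraph goes on to allow abstinence at the investigator's discretion and to require contraception during the study and for 2 months after the drug is stopped.

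The protocol summary shortens the criterion to "Pregnant or nursing woman or woman of child-bearing potential not using effective contraception".

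**The concern.** Both sections use the term highly effective, so they cannot be read as two tiers of protection. They should agree on which methods qualify, who is of child-bearing potential and when a woman is post-menopausal. They differ on all three, the second only if the 8.4.3 sentence is taken literally.

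Sections 4.5 and 7 say that the effect of treatment on a fetus is unknown and make participation conditional on following the contraception requirements. Section 4.5 locates those requirements in the protocol, which contains two sets. Sections 9.1.1 and 10.1.4 require study treatment to stop if a participant becomes pregnant. What is at stake is consistent eligibility and consistent protection of participants across the 10 to 15 centers.

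**Working it through.** No arithmetic applies and the plan states no figure to reproduce. The check sets the two sections side by side.

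| Item | Section 5.2, criterion 14 | Section 8.4.3 |
|---|---|---|
| Double-barrier methods | Not listed | Listed as highly effective |
| Intrauterine device or system | Listed | Not listed |
| Hormonal methods | Listed with conditions (failure rate below 1% for other forms; at least 3 months on the same pill) | Listed without conditions |
| Sterilization | Listed | Listed |
| Total abstinence | Listed as highly effective, if it fits the participant's usual lifestyle | Acceptable at the investigator's discretion |
| Post-menopausal | 12 months of amenorrhea | 12 months, or 6 months with FSH above 40 |
| Contraceptive users | Within child-bearing potential | Inside the exception, if the sentence is taken literally |

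1. *Methods.* The conflict runs both ways. A woman relying only on double-barrier methods satisfies the 8.4.3 list but uses nothing that criterion 14 names. A woman with an intrauterine device satisfies criterion 14 but uses nothing that 8.4.3 names as highly effective.

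2. *Post-menopausal status.* A woman with 6 to 12 months of amenorrhea and FSH above 40 is post-menopausal under 8.4.3. Under criterion 14 she is not, so unless she is surgically sterile she needs a listed method.

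3. *Child-bearing potential.* The 8.4.3 sentence has no main clause. As printed, its final limb on contraceptive users hangs on the same *unless* as the menopause and surgery limbs. A contraceptive user would then fall outside the definition. In criterion 14 she stays inside it, and her contraception is what makes her eligible.

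4. *Pregnancy testing.* Section 8.4.3 exempts only women documented as surgically sterile or as post-menopausal for at least 12 months before screening. Contraceptive users are not exempt, and neither is a woman on the 6-month route. Table 8-1 schedules the pregnancy and fertility assessment at Screening and from Month 1 onward. The conflicts in steps 1 to 3 do not reach this exemption.

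**The case against.** The strongest reply is that Section 5.2 governs enrolment and 8.4.3 only describes assessments, so a careful site would apply criterion 14. The log for Amendment 02 records that the definition of highly effective contraception was clarified in Section 5.2, so 8.4.3 may simply be leftover text. Criterion 14 also introduces its methods with *include*, which does not expressly close the list. And the summary gives only key criteria in short form.

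Part of this stands. Enrolment errors are possible rather than likely, and the summary wording is a minor point. The conflict remains, though. The only opening that criterion 14 leaves to unlisted methods is for other hormonal forms, so nothing in it admits barrier methods. Section 8.4.3 is also where contraception during the study and for 2 months afterwards is required, so sites have reason to work from it once a woman is enrolled.

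Two stronger readings are tempting. A reader might infer that the protocol deliberately treats contraceptive users as not of child-bearing potential. The incomplete sentence looks more like an exclusion statement that lost its opening, and the same paragraph goes on to require contraception, which would make little sense if users were exempt. A reader might also infer that such women could skip the screening pregnancy test; the exemption in the same section rules that out.

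**Conclusion.** Wrong as written: an internal contradiction between Sections 5.2 and 8.4.3. The differences in the method lists and in the post-menopausal definition hold however the 8.4.3 sentence is parsed. The difference on child-bearing potential rests on its literal wording and is probably a drafting error.

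A site using 8.4.3 could accept, or keep on drug, a woman relying only on double-barrier methods, or turn away a user of an intrauterine device or system whom criterion 14 accepts. The women directly concerned by the method lists are these two groups, not all users of barrier methods: 8.4.3 names only double-barrier methods. The documents give neither the number of women of child-bearing potential expected among the approximately 100 participants nor the methods they use, so no count is stated.

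The protocol describes the fetal risk as unknown. It would be an overstatement to rest the point on an established fetal risk. There is no effect on the sample size or the primary analysis.

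**What to change.** Reconcile Sections 5.2 and 8.4.3 so that the protocol carries one list of acceptable methods, one definition of child-bearing potential and one definition of post-menopausal status. Rewrite the incomplete sentence in 8.4.3, or replace it with a cross-reference to criterion 14 as reconciled. Align the summary with the agreed wording. Which version is clinically right is for the sponsor to decide.

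The cost is a wording change in three places, made through a protocol amendment, and a check that the consent form states the same requirements. No analysis needs to change.
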